7.6. Special Instructions Regarding Treatment of Toxicity

Infusion-Related Toxicity and Hypersensitivity:

Careful attention to prophylaxis and bedside monitoring of vital signs is recommended. Discontinue therapy for anaphylaxis. Mild symptoms: (e.g., mild flushing, rash, pruritus): complete infusion, supervise at bedside. No treatment required. Panitumumab is contraindicated in patients with a history of life-threatening hypersensitivity reaction to panitumumab or any of the excipients.

Moderate Symptoms: (e.g., moderate rash, flushing, mild dyspnea, chest discomfort): Stop chemotherapy infusion. Give intravenous diphenhydramine 25 mg and intravenous dexamethasone 10 mg. Resume infusion after recovery of symptoms at a low rate of infusion, 20 mg/hr for 15 minutes. Then, if no further symptoms develop, resume infusion at full dose rate until infusion has been completed. If symptoms recur, stop infusion. Remove patient from protocol therapy. Report as an adverse event.

Severe Life-threatening Symptoms: (e.g., hypotension requiring pressor therapy, angioedema, respiratory distress requiring bronchodilator therapy, generalized urticaria): Stop infusion. Give intravenous diphenhydramine and dexamethasone, as indicated above. Add epinephrine and / or bronchodilators if indicated. If wheezing is present and is not responsive to adrenaline, then administer 0.35 ml of nebulized salbutamol solution (or equivalent). Remove patient from protocol therapy. Report as an adverse event.

Diarrhea

Irinotecan can cause diarrhea, and should be *stopped at diarrhea grade ≥ 2* , and treated symptomatically (recommend IV hydration and use of loperamide for diarrhea, observing loperamide dosage recommendation and treatment start, see below). If control takes longer than 2 days, medical evaluation including relevant diagnostic procedures, alternative treatment and possible investigation of DPD deficiency should be considered. Irinotecan cannot be re-started until diarrhea has resolved to grade < 2 with the last loperamide dose given at least 24 hours beforehand.

The recommended dosage regimen for loperamide: 4 mg at the first onset of late diarrhea and then 2 mg every 2 hours until the patient is diarrhea-free for at least 12 hours. During the night,

the patient may take 4 mg of loperamide every 4 hours. Note: This dosage regimen exceeds the usual dosage recommendations for loperamide. Premedication with loperamide is not recommended.

The use of drugs with laxative properties should be avoided because of the potential for exacerbation of diarrhea. Patients should be advised to contact their physician to discuss any laxative use.

Grade \geq 2 Nausea/Vomiting

For nausea and vomiting the patients must be supplied with anti-emetics in order to help themselves in case nausea or vomiting occurs at home. The choice and dose of anti-emetics will be determined by the treating physician. Adequate secondary prophylactic treatment and IV hydration should be initiated once nausea or vomiting has occurred. If the adverse event recurs despite prophylaxis, then dose modifications should also be according to the table above.

Fever/Infection with or without neutropenia

Chemotherapy should be stopped immediately. Appropriate anti-infective therapy should be initiated. When the ANC has recovered to $\geq 1,500/\text{mm}^3$ and the fever or infection has resolved, the patient may restart treatment.

Skin Toxicity

With panitumumab, various degrees of skin toxicity, specifically rash and erythema have been reported. Topical emollients have been used with some success in mild cases. If the rash were to develop to have small acneiform pustules, topical antibiotic ointments have been used with varying amounts of success as well. The rash is self-limiting and dissipates upon cessation of the drug in the majority of cases.

It is recommended patients use sunscreen and hats to limit sunexposure while on receiving panitumumab.

Pulmonary Toxicity

Panitumumab may cause pulmonary fibrosis. In case of unexplained respiratory symptoms such as non-productive cough, dyspnea, crackles, or radiological pulmonary infiltrates, panitumumab should be discontinued until further pulmonary investigation.

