7.2. Protocol Dosage Regimen and Administration

Prophylactic Skin Treatment: The day before treatment is initiated, patients will be given minocycline at a dose of 100 mg PO bid followed by daily minocycline at a dose of 100 mg PO qd for the duration of therapy. In the STEPP study (Piperdi et al, Abs 394, ASCO GI 2009), patients who received prophylactic therapy (doxycycline) had a significant reduction in the incidence and severity of rash. There was also an improvement in the risk of diarrhea when panitumumab was added to irinotecan in the presence of a prophylactic strategy.

If patient experiences reaction to minocycline, it will be discontinued. The trial will proceed without modification.

It is also recommended patients wear sunscreen and hats and limit sun exposure.

On days one and 15 of a cycle the following drugs will be administered: Irinotecan 180 mg/m², 5-FU 400 mg/m² bolus, leucovorin 200 mg/m², panitumumab 6 mg/kg. Finally the patient will be given a pump to continue to receive their infusional 5-FU at a total dose of 2400mg/M² over 46 hours. Panitumumab will be administered first on each treatment day. A cycle of therapy is 28 days and the regimen is repeated on Day 29.

Of note: if a patient has required dose reduction of FOLFIRI chemotherapy with their previous administrations, then such dose reductions will continue at the time of enrollment in this protocol with the exceptions of **sub-optimally** controlled nausea, vomiting, diarrhea, neutropenia, and anemia. Patients with more than 50% reduction of the original dose of infusional 5FU and/or irinotecan will not be allowed on the study (see section 4.2.9). The aforementioned side effects should be attempted to be controlled with the appropriate supportive measures and the full dose of irinotecan should be given.

Premedication for chemotherapy may be administered prior to, during, or after panitumumab administration (if given during panitumumab administration, pre-medications should be given through a separate IV line). Panitumumab will be administered until subjects develop disease progression or are unable to tolerate panitumumab.

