- All dose adjustments are relative to dose given at on day #1 of that cycle.

FOLFIRI Regimen Dose Modification Guideline^a

Dose Modifications for the Next Cycle Based on the Worst Toxicity Observed ^{b,f}		
Toxicity Grade ^b (CTCAE v4.0)	5-FU bolus and continuous infusion	Irinotecan
Neutropenia, Thrombocytopenia, and Leukopenia (since prior treatment)		
0 or 1	Maintain dose level	Maintain dose level
2	Discontinue 5-FU bolus	Maintain dose level
3	Discontinue 5-FU bolus and ↓ 1 dose level continuous infusion	↓ 1 dose level
4	Discontinue 5-FU bolus and ↓ 2 dose levels continuous infusion	↓ 2 dose levels
Neutropenic fever or infection ^c	Discontinue 5-FU bolus and ↓ 2 dose levels continuous infusion	↓ 2 dose levels
Diarrhea ^d (since prior treatment)		
0 or 1	Maintain dose level	Maintain dose level
2	Discontinue 5-FU bolus and ↓ 1 dose level continuous infusion	Maintain dose level
3	Discontinue 5-FU bolus and ↓ 1 dose level continuous infusion	↓ 1 dose level
4	Discontinue 5-FU bolus and ↓ 2 dose levels continuous infusion	↓ 2 dose levels
Mucositis/Stomatitis (since prior treatment)		
0, 1 or 2	Maintain dose level	Maintain dose level
3	Discontinue 5-FU bolus	Maintain dose level
4	Discontinue 5-FU bolus and ↓ 1 dose level continuous infusion	Maintain dose level
Vomiting (since prior treatment)		
0, 1 or 2	Maintain dose level	Maintain dose level
3	Maintain dose level	↓ 1 dose level
4	Discontinue 5-FU bolus ↓ 1 dose level continuous infusion	↓ 1 dose level

Palmar-plantar erythrodysesthesia			
0, 1 or 2	Maintain dose level	Maintain dose level	
3	Discontinue 5-FU bolus ↓ 1 dose level continuous infusion	Maintain dose level	
Other nonhematologic toxicities (except alopecia and skin-related toxicities) ^e			
0, 1 or 2	Maintain dose level	Maintain dose level	
3	Discontinue 5-FU bolus ↓ 1 dose level continuous infusion	↓ 1 dose level	
4	Discontinue 5-FU bolus ↓ 2 dose levels continuous infusion	↓ 2 dose levels	

^a There will be no leucovorin dose reduction. If 5-FU bolus dropped, leucovorin will be discontinued as well.

^b NCI CTCAE(Version 4.0) (Appendix E)

^c Absolute Neutrophil Count <1000/mm³ and Temperature ≥ 38.5°C

^d Despite maximum supportive care

^e Bilirubin grade 3 and grade 4 hold dose: once the bilirubin level has resolved to ≤ grade 1 a dose reduction for 5-FU and irinotecan is required.

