^f If the patient's starting dose upon enrollment is not full dose FOLFIRI, future dose adjustments will be made as to reflect the starting dose (i.e. proceed to the next recommended dose)

*There will be no leucovorin dose reduction. If bolus 5-FU dose omitted, leucovorin is also omitted

Table 2. FOLFIRI Regimen Dose Levels (mg/m²)

DRUG	Starting Dose (mg/m ²)	Dose Level -1 (mg/m ²)	Dose Level -2 (mg/m ²)	Dose Level -3 (mg/m ²)
Irinotecan	180	150	120	Discontinue
5-FU 46 hour infusion	2400	2000	1600	Discontinue

7.5. Panitumumab Dose Modification for Toxicity- (Please refer to Table 3).

The starting panitumumab dose is 6 mg/kg every 2 weeks. The total dose may be rounded up or down by no greater than 10 mg. The panitumumab dose will be calculated based on the subject's actual body weight at baseline and will not be re-calculated unless the actual body weight changes by at least 10%. Panitumumab will be diluted in a minimum of 100 mL of pyrogen-free 0.9% sodium chloride solution USP/PhEur (normal saline solution, supplied by the site). The maximum concentration of the diluted solution to be infused should not exceed 10 mg/mL. The

volume of normal saline should be increased as needed to ensure the maximum concentration of the diluted solution does not exceed 10 mg/mL. Panitumumab will be administered IV by an infusion pump through a peripheral line or indwelling catheter using a 0.22-micron in-line filter infusion set-up over 1 hour ± 15 minutes by a trained healthcare professional. If the first infusion is well tolerated (ie without any serious infusion-related reactions) all subsequent infusions may be administered over 30 ± 10 minutes. In the event a subject's actual weight requires greater than 150 mL volume infusion, panitumumab will be administered over 60 to 90 minutes ± 15 minutes, as tolerated.

The bag should be labeled per site pharmacy Standard Operating Procedures and promptly forwarded to the clinical research center for infusion.

The effects of overdose of panitumumab are not known.

See Appendix 6 Pharmacy Guide for information on panitumumab packing and formulation, labeling, storage, preparation, supply/return, and accountability.

Pre-medication for Panitumumab

Panitumumab specific pre-medication is not required for routine panitumumab infusions. If, during or after any infusion, a reaction occurs, pre-medication may be used for subsequent panitumumab infusions according to institutional guideline or investigator's discretion.

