Interruption of Panitumumab Infusion

Subjects who experience any serious infusion reaction during panitumumab administration will have the infusion stopped. Continuation of dosing will be based on the severity and resolution of the event and will be at the discretion of the investigator. Suspected infusion reactions should be reported as an adverse event. All subjects who experience such an event will be followed for safety.

Toxicity Assessment

Toxicities will be recorded as adverse events on the Adverse Event case report form and must be graded using The National Cancer Institute's Common Toxicity Criteria (CTCAE) version 4.0 (Appendix 4), with the exception of skin- or nail-related toxicities, which must be graded using CTCAE version 3.0 with modifications (see Appendix 4a).

Panitumumab Dosage Adjustments

For subjects who experience toxicities while on study, one or more doses of panitumumab may need to be withheld, reduced, or delayed (administered at > 14 day intervals). On resolution of toxicity, a limited number of attempts to re-escalate reduced panitumumab doses will be allowed (outlined in Figure 4). Dose escalations above 6 mg/kg starting dose are not allowed. Panitumumab dose reductions are listed in Table 3.

Table 3. Panitumumab Dose Reductions

	Starting Dose	1 st Dose Reduction	2 nd Dose Reduction
Percentage (%)	100	80	50
mg/kg	6	4.8	3.0

Criteria for Withholding a Dose of Panitumumab

Skin- or nail-related toxicities:

- Symptomatic skin- or nail-related toxicity requiring narcotics, systemic steroids, or felt to be intolerable by the subject
- Skin or nail infection requiring IV antibiotic or IV antifungal treatment
- Need for surgical debridement
- Any skin- or nail-related serious adverse event

Non-skin- or nail-related toxicities:

Any grade 3 or 4 toxicity with the following exceptions:

- Panitumumab will only be withheld for symptomatic hypomagnesemia and/or hypocalcemia that persists despite aggressive magnesium and/or calcium replacement
- Panitumumab will only be withheld for grade 3 or 4 nausea, diarrhea, or vomiting that persists despite maximum supportive care (see Section 6.6 and 6.7.1 for diarrhea management guidelines)
- Panitumumab will only be withheld for grade ≥ 3 anemia or grade 4 thrombocytopenia that can not be managed by transfusion(s) or cytokine therapy

Criteria for Re-treatment with Panitumumab

Skin- or nail-related toxicities:

- Panitumumab administration may recommence once:

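### Sections 7.4 and 7.6 can give different chemotherapy doses after a first episode of grade 3–4 vomiting

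*Combined protocol and SAP*

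**What the plan says.** The FOLFIRI grid in section 7.4 is headed "Dose Modifications for the Next Cycle Based on the Worst Toxicity Observed". Its vomiting row leaves doses unchanged up to grade 2. At grade 3 it lowers irinotecan by one level and keeps 5-FU. At grade 4 it stops the 5-FU bolus and lowers both the infusion and irinotecan by one level. Under the grid's footnote a, leucovorin stops when the bolus stops. The row does not distinguish a first episode from a later one. The supportive-care qualifier, footnote d ("Despite maximum supportive care"), is attached to diarrhea only.

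The nausea and vomiting paragraph of section 7.6 is headed for grade 2 and above. After an event it calls for secondary prophylaxis and intravenous hydration. It then adds: "If the adverse event recurs despite prophylaxis, then dose modifications should also be according to the table above".

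For comparison, the panitumumab rules in section 7.5 do carry a supportive-care condition for these events: "Panitumumab will only be withheld for grade 3 or 4 nausea, diarrhea, or vomiting that persists despite maximum supportive care".

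**The concern.** The two sections address the same event and put dose reduction at different points. The grid acts on any grade 3 or 4 vomiting since the prior treatment. Section 7.6 puts prophylaxis first and brings in the table if the event comes back. A site working from the grid would reduce chemotherapy after the first episode. A site working from 7.6 would not.

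What is at stake is the dose delivered and the safety record. This is a single-arm trial of 25 patients at two institutions, and the frequency and severity of toxicity is a secondary objective. If the dose after a first severe episode depends on which page was consulted, later toxicity is observed under two different rules and no control arm shows the difference.

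Section 7.2 makes the situation foreseeable. Patients whose earlier FOLFIRI reductions were for poorly controlled nausea or vomiting do not carry those reductions into the study.

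**Working it through.** No figure in the statistical section bears on this point. The check applies each section's rule to the same event and compares the resulting doses.

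**Inputs**
- Starting doses (section 7.2): "Irinotecan 180 mg/m², 5-FU 400 mg/m² bolus, leucovorin 200 mg/m², panitumumab 6 mg/kg", plus a 46-hour 5-FU infusion of 2400 mg/m².
- Dose levels (Table 2): irinotecan 180, 150, 120 mg/m²; infusion 2400, 2000, 1600 mg/m².
- Steps for each grade: the vomiting row of the 7.4 grid.
- Total 5-FU = bolus + infusion. At full dose this is 400 + 2400 = 2800 mg/m².

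**First episode, from full starting dose (mg/m²)**

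| Event | Drug | 7.4 grid | 7.6, natural reading | Grid relative to 7.6 |
|---|---|---|---|---|
| Grade 2 | irinotecan | 180 | 180 | none |
| Grade 2 | total 5-FU | 2800 | 2800 | none |
| Grade 3 | irinotecan | 150 | 180 | 1 − 150/180 = 16.7% lower |
| Grade 3 | total 5-FU | 2800 | 2800 | none |
| Grade 4 | irinotecan | 150 | 180 | 16.7% lower |
| Grade 4 | total 5-FU | 0 + 2000 = 2000 | 2800 | 1 − 2000/2800 = 28.6% lower |
| Grade 4 | leucovorin | stopped | 200 | stopped against given |

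The 28.6% pools the bolus and the infusion. The infusion alone falls by 1 − 2000/2400 = 16.7%.

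**Recurrence.** If each grade 3 event takes a further step, the grid gives irinotecan 150 and then 120 mg/m². The 7.6 sequence gives 180 and then 150. A second episode therefore leaves the two one level apart. If there is no second episode, the first difference persists, because section 7.4 states no rule for raising chemotherapy doses again.

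**Does the recurrence condition do any work?** If the grid already governs every grade 3–4 episode, including the first, then making dose modification conditional on recurrence adds nothing. The condition has an effect only if a first episode is handled differently. That is why prophylaxis first, then the table, is the natural reading.

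**Nausea.** Section 7.6 covers nausea as well as vomiting and sends both to the table, but the grid has no nausea row. The only row that can hold it is the catch-all for other nonhematologic toxicities. At grade 3 that row stops the bolus and lowers the infusion and irinotecan by one level each: total 5-FU 2000 and irinotecan 150 mg/m². The vomiting row at grade 3 gives 2800 and 150. The row a reader picks for nausea therefore changes the 5-FU dose, and 7.6 does not say which row is meant.

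**The case against.** The strongest reply is that 7.6 does not suspend the grid for a first event. It says what happens on recurrence, and its word *also* may mean that recurrences follow the table too, just as first episodes do. On that reading there is no conflict. This stands as a possible reading, and it is why the text cannot be said to forbid a reduction after a first episode. It does leave the recurrence condition with nothing to do, so it does not settle the matter.

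A second reply is that 7.6 gives special instructions that qualify a grid labelled as a guideline. That would be a workable order of precedence, but neither section states it, and the vomiting row has no pointer to 7.6.

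Three stronger inferences are tempting, and the documents do not support them:
- **That the conflict starts at grade 2, because of the 7.6 heading.** The grid leaves doses unchanged at grade 2, so following the table there changes nothing.
- **That the grid contradicts itself by treating nausea more severely than vomiting.** Nausea is covered by the catch-all row, and different reductions in different rows are a clinical choice. At grade 3 only 5-FU differs; irinotecan drops one level in both rows. Section 7.4 also lets the investigator continue unchanged for toxicities judged unlikely to become serious. What remains is the missing pointer from 7.6.
- **That the grid demands an immediate cut.** Its heading speaks of the next cycle and the Table 1 caption of day 15. The grid acts on the next doses, and those two labels do not agree on which.

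The panitumumab rule concerns another drug. It shows that the plan attaches a supportive-care condition where it wants one, but it does not contradict the chemotherapy grid.

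**Conclusion.** The point holds for a first episode of grade 3–4 vomiting. On the natural reading of 7.6, the two sections give irinotecan 150 against 180 mg/m². At grade 4 they also give total 5-FU 2000 against 2800 mg/m², with leucovorin stopped under the grid. On the weaker reading the sections agree, but the text does not tell a site which reading applies. It is an inconsistency in a stated rule that affects delivered dose and safety.

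The doses assume a full starting dose. Patients may enter at a reduced dose, and the grid's footnote f then counts steps from there. For example, a patient starting at irinotecan 150 would face 120 against 150 mg/m² (1 − 120/150 = 20% lower).

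A reader might infer that progression-free survival would be biased. The documents do not support a figure: they give no rate of grade 3–4 vomiting in this setting and no relation between dose and outcome. The number of patients affected is therefore also left open. The sample size of 25 does not depend on this point.

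**What to change.** Reconcile the vomiting row of the 7.4 grid with the nausea and vomiting paragraph of 7.6, so that one instruction governs both a first grade 3–4 episode and a recurrence. In 7.6, identify the table by name, since it is now given only by position and the nearest numbered table above it is Table 3, for panitumumab. State which grid row applies to nausea. Which rule applies is for the clinical lead to decide.

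The cost is a footnote in the grid and a sentence in 7.6. No design figure changes.

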7.7. Supportive Therapy

7.7.1. Diarrhea

Loperamide: All patients will be instructed to begin taking loperamide at the earliest signs of diarrhea (i.e. first poorly formed or loose stool, first episode of two or more bowel movements in one day) that occurs more than 12 hours after receiving irinotecan. Loperamide should be taken in the following manner: 4 mg at the first onset of diarrhea, then 2 mg every 2 hours around-the-clock until diarrhea-free for at least 12 hours. Patients may take loperamide 4 mg every 4 hours during the night.

Atropine: Diarrhea or abdominal cramping that occurs during or within one hour after receiving irinotecan should be treated with atropine 0.4 mg IM or Subq. Additional antidiarrheal measures may be used at the discretion of the treating physician. Atropine should be used with caution in

patients with potential contraindications (e.g., obstructive uropathy, glaucoma, tachycardia, etc.).

7.7.2. Nausea and Vomiting

Antiemetics: Patients should receive antiemetics prior to chemotherapy administration according to institution guidelines.

7.7.3. Myelosuppression

Growth Factors: Routine prophylactic use of a colony-stimulating factor (G-CSF or GM-CSF) is not permitted. Therapeutic use in patients with serious neutropenic complications such as ANC of < 500 for more than 5 days, fever accompanying grade 3-4 neutropenia, or obvious sepsis may be considered, at the investigator's discretion.

Erythropoietin treatment for moderate to severe anemia (< 10 mg/dl) is permitted in the study.

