4. SELECTION CRITERIA

4.1. Inclusion Criteria

To be eligible for inclusion, each patient must fulfill each of the following criteria:

1. Patients with advanced adenocarcinoma of the colon or rectum not curable with surgery or radiotherapy and have been previously treated for their disease with FOLFIRI plus bevacizumab in the **first line** metastatic setting. Patients will only be eligible if their last line of therapy prior to enrolling onto the study was FOLFIRI and bevacizumab received **no more than 6 months prior** to enrolling in this study. They should have been treated with FOLFIRI plus bevacizumab until disease progression is radiographically documented
2. Patients' tumors will need to be tested for the *RAS* mutation status. Only those patients with wild-type or unmutated *RAS* oncogene are eligible to participate in this study.
3. Provide written informed consent prior to study-specific screening procedures, with the understanding that the patient has the right to withdraw from the study at any time, without prejudice.
4. Prior cetuximab is allowed in the **adjuvant but not in the metastatic setting**, but must have been **completed at least 6 months** before enrolling on this trial.
5. Age \geq 18 years
6. ECOG performance status \leq 1
7. Life expectancy greater than 12 weeks

8. No active brain metastasis. Previously surgically treated or irradiated lesions are allowed if not clinically active.
9. Has a negative serum pregnancy test within 7 days of first dose of study treatment (female patients of childbearing potential).
10. Ability to understand and willingness to sign a written informed consent
11. No history of severe reactions to 5-FU, irinotecan, or a monoclonal antibody
12. Adequate organ and marrow function as defined below:

Leukocytes	$\geq 3000/\mu\text{L}$
Absolute neutrophil count	$\geq 1500/\mu\text{L}$
Platelets	$\geq 100,000/\mu\text{L}$
Hemoglobin	$\geq 9\text{ mg/dL}$
Total Bilirubin	$\leq 1.5 \times \text{ULN}$
AST/ALT	$\leq 3 \times \text{ULN}$ (or $< 5 \times \text{ULN}$ with liver metastases).
Creatinine Clearance	(CrCl) $\geq 30 \text{ ml/min}$ (Cockcroft-Gault Equation)
Magnesium	\geq lower limit of normal
13. Measurable disease is required according to RECIST 1.1 criteria (45).

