5. REGISTRATION PROCEDURES

Subsite patients will have eligibility verified and will be centrally registered at The Ohio State University by the OSU Subsite Coordinator. Subsites should call or email the OSU Subsite Coordinator to verify enrollment availability prior to consenting patients.

Following registration, patients should begin protocol treatment within 5 business days. Issues that may cause treatment delays should be discussed with the OSU Principal Investigator as soon as possible. If a patient does not receive protocol therapy following registration, the patient will be replaced. The OSU Subsite Coordinator must be notified immediately if a patient does not receive protocol therapy.

Only patients deemed eligible by the subsite research team should be sent for eligibility verification and registration by the OSU Subsite Coordinator.

To request patient registration, the documents below must be completed by the subsite research team and faxed or securely emailed to the OSU Subsite Coordinator. If secure email is the preferred method and the subsite does not have a confirmed secure email system, the OSU secure email system may be used. Contact the OSU Subsite Coordinator for more information.

Required documents for registration:

- Enrollment Form (Appendix 5)
- Signed Eligibility Checklist (Appendix 6)
- Source documents verifying every inclusion & exclusion criteria
- Required screening items as listed in the Protocol Calendar. Screening tests must be

within the specified window.

- Emails and other signed forms used as source documentation

The OSU Subsite Coordinator will confirm receipt of the registration documents with the subsite contact listed on the Enrollment Form (Appendix 5). If confirmation is not received within 2 hours, it is strongly recommended that the subsite call the OSU Subsite Coordinator to confirm registration documents were received.

Registration requests will be processed as soon as possible and no later than 1 business day after receipt of the registration documents, pending there is no additional information needed to complete eligibility verification. Patients will be registered immediately upon determining they meet eligibility criteria.

The Subsite Coordinator will securely email the subsite contact listed on the Enrollment Form (Appendix 5) with the registration confirmation, and the patient's assigned study number.

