6.7. Safety Parameters

6.7.1. Laboratory Tests

Laboratory tests during treatment will be performed according to the Schedule of Assessments and Procedures.

The following laboratory tests during treatment will be performed according to the Schedule of Assessments and Procedures.

- Complete Blood Count including differential, WBC, RBC, hemoglobin, hematocrit, platelet count
- Total bilirubin, AST/ALT, alkaline phosphatase, albumin, and total protein
- Conjugated (direct) bilirubin in the case of abnormal total bilirubin
- Serum creatinine and uric acid
- Glucose
- Electrolytes (sodium, potassium, magnesium)

- Serum calcium and inorganic phosphate
- Urinalysis (pH, protein, glucose and blood) (as clinically indicated)

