7.4. Dose Adjustment for 5FU and Irinotecan Toxicities

A cycle is 4 weeks – with treatment on days 1 and 15. We do not make up day #15 treatments if a patient should require adjustment or omission based on outlined criteria below.

- This study will take into consideration previous toxicities experienced with FOLFIRI prior to enrollment. The initial dose of FOLFIRI will be determined by the investigator at time of trial initiation. Prior to enrollment, if the patient experienced significant toxicity with FOLFIRI and dose adjustments were required, these dose adjustments will continue upon initiation of this trial.
- For toxicities which are considered by the investigator unlikely to develop into serious or life-threatening events (e.g. alopecia, altered taste etc.), treatment will be continued at the same dose without reduction or interruption. In addition, no dose reductions or interruptions will be required for anemia as it can be satisfactorily managed by transfusions.
- For any event that is apparent at baseline, the dose modifications will apply according to the corresponding shift in toxicity grade, if the investigator feels it is appropriate. (e.g. if a patient has grade 1 asthenia at baseline which increases to grade 2 during treatment, this will be considered as a shift of 1 grade and treated as a grade 1 toxicity for dose modification purposes).
- If on the first day of chemotherapy treatment, the granulocyte count (ANC) is < 1,500 or the platelet count is < 75,000, treatment will be held for up to three weeks until ANC is ≥ 1200 and platelet count is ≥ 75,000. CBC should be obtained at least weekly when treatment is held. Chemotherapy doses will not be reduced based on nadir counts except in febrile neutropenia as defined below.
- If the dose is modified to manage an adverse event, it is recommended that the patient be seen by the investigator prior to re-starting study drug.
- If a rest period is extended due to toxicity, the "complete" cycle should be given afterwards with chemotherapy and panitumumab. If toxicity requires a dosing delay/interruption of both 5-FU and irinotecan of more than six weeks or at the

discretion of the investigator, the patient will be withdrawn from the study for toxicity reasons.

Table 1: Dose modifications during a course of therapy (day #15 of each cycle).

- Dose adjustments for hematological toxicity during a course of therapy are based on the blood counts obtained in preparation for that day of treatment.

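### Both hemoglobin limits that carry a unit (inclusion criterion 12 and Section 7.7.3) are printed in mg/dL instead of g/dL, so the written eligibility floor is 1000-fold too low

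*Combined protocol and SAP*

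**What the plan says.** Section 4.1, inclusion criterion 12, introduces a list of laboratory limits with the words "Adequate organ and marrow function as defined below". The list has eight rows: leukocytes, absolute neutrophil count, platelets, hemoglobin, total bilirubin, AST/ALT, creatinine clearance and magnesium. The hemoglobin row requires at least 9 mg/dL.

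Section 7.7.3, on supportive care for myelosuppression, says: "Erythropoietin treatment for moderate to severe anemia (< 10 mg/dl) is permitted in the study". It does not name hemoglobin, but an anemia limit expressed per deciliter can hardly mean anything else.

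The other rules that mention hemoglobin or anemia give no hemoglobin value:

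- Section 6.7.1 lists hemoglobin as one component of a laboratory panel: "Complete Blood Count including differential, WBC, RBC, hemoglobin, hematocrit, platelet count".
- Section 7.4, on chemotherapy doses, says "no dose reductions or interruptions will be required for anemia as it can be satisfactorily managed by transfusions".
- Section 7.5, on withholding panitumumab, uses a toxicity grade: "Panitumumab will only be withheld for grade ≥ 3 anemia or grade 4 thrombocytopenia that can not be managed by transfusion(s) or cytokine therapy".

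Section 5 lists what a subsite must send for central registration. The list includes a signed eligibility checklist and "Source documents verifying every inclusion & exclusion criteria".

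**The concern.** A hemoglobin of 9 mg/dL is not a possible clinical threshold. The values 9 and 10 are plausible in g/dL, and the second is attached to a description of moderate or worse anemia, so g/dL must have been intended. The same wrong unit appears in two separate sections, with different capitalization (mg/dL and mg/dl), so an error in reading the PDF is an unlikely explanation.

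The eligibility row matters more than the erythropoietin sentence. Inclusion criterion 12 is binding on every patient, and it is the only numeric hemoglobin limit on starting treatment. The first-day treatment rules in Section 7.4 set neutrophil and platelet thresholds but no hemoglobin value. Taken as printed, the criterion is met by a patient with marked anemia. If such a patient were registered, the protocol text would not support calling it a deviation.

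**Working it through.** The two limits are stated thresholds, not results of a calculation, so there is no figure of the plan's own to reproduce. The check is a unit conversion and a search for any value that would settle the unit.

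**Inputs**

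- Entry floor: hemoglobin ≥ 9 mg/dL (Section 4.1, criterion 12).
- Erythropoietin limit: < 10 mg/dl (Section 7.7.3).
- Conversion: 1 g = 1000 mg.

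**Conversion**

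| Limit | As printed | Printed value in g/dL | Evident intent | Intent in mg/dL | Ratio of intent to print |
|---|---|---|---|---|---|
| Criterion 12 | ≥ 9 mg/dL | 9 / 1000 = 0.009 | ≥ 9 g/dL | 9 × 1000 = 9,000 | 9,000 / 9 = 1000 |
| Section 7.7.3 | < 10 mg/dl | 10 / 1000 = 0.010 | < 10 g/dL | 10 × 1000 = 10,000 | 10,000 / 10 = 1000 |

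**Consequence of a literal reading**

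- Any hemoglobin from 0.009 g/dL up to, but not including, 9 g/dL passes the printed floor and fails the intended one. That range covers every patient the criterion is meant to exclude.
- Illustration with an assumed value, since the documents report no patient data: 7 g/dL = 7,000 mg/dL, and 7,000 / 9 = 778, so this patient clears the printed floor 778-fold. Assumed values of 5 and 8 g/dL give 5,000 / 9 = 556 and 8,000 / 9 = 889. All three fail a floor of 9 g/dL.
- For erythropoietin, the same assumed 7 g/dL (7,000 mg/dL) is not below 10 mg/dL. The printed limit is therefore not met by a patient who is clearly anemic.

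**Search for a correcting value**

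- Hemoglobin limits with a unit: two, in criterion 12 and Section 7.7.3. Both are in milligrams.
- Sections 6.7.1, 7.4 and 7.5 give a test name, a rule without a number and a toxicity grade, respectively. None supplies a value.
- The unit g/dL does not appear anywhere in the document.
- One of the eight laboratory rows in criterion 12 is affected.

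**Effect on the statistics**

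Neither limit enters the calculation in Section 10.1, so the 25 patients, the one-sided type I error of 0.10 and the stated 80% power do not depend on this correction.

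**The case against.** The strongest reply is that no qualified reader would be misled. The criterion's lead-in says it defines adequate marrow function, which a floor met by every living patient plainly would not do. Section 7.7.3 explains its own number in words. Laboratories and clinicians work in g/dL, and nobody would convert a report to mg/dL before comparing it with 9. There are also backstops: exclusion criterion 17 lets the investigator exclude serious uncontrolled medical conditions, and Section 5 has subsite eligibility verified centrally. On treatment, anemia is handled by transfusion or by toxicity grade, not by the misprinted number. The eligibility checklist that sites complete was not in the text available, so it may already carry the right unit. On this view the point is editorial.

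Much of this stands. The practical effect is small, erythropoietin is not prohibited by the misprint, and there is no evidence that any patient was wrongly enrolled. But neither backstop is a numeric hemoglobin limit: exclusion 17 rests on judgment, and central verification checks patients against the criteria as written. A binding entry threshold should be correct on the page without relying on each reader to amend it silently.

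**Conclusion.** The error is real. Both hemoglobin limits that carry a unit are too small by a factor of 1000, and inclusion criterion 12, followed exactly as written, excludes no one. The weight rests on the eligibility row; Section 7.7.3 is a second instance of the same slip, with little consequence of its own.

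The expected effect on the trial is small, and no design or analysis quantity changes. The number of screened patients who could be affected cannot be estimated, because the documents give neither a screening count nor a hemoglobin distribution.

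The conclusion rests on two inferences, both secure: that g/dL was intended, because 9 and 10 are plausible only in that unit, and that the limit in Section 7.7.3 refers to hemoglobin.

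**What to change.** Change the unit to g/dL in the hemoglobin row of inclusion criterion 12 and in Section 7.7.3, keeping the values 9 and 10. In Section 7.7.3 it would also help to name hemoglobin. Confirm that the eligibility checklist (cited in Section 5 as Appendix 6) uses g/dL.

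The cost is one unit changed in two places, carried in the next amendment, plus one check of the checklist. Sample size, conduct and analysis are unaffected.
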